| | | | | | | | | | | | | | 55 years in first degree relatives only See Section 8.1.2 for more information |
| Prior ART check to ensure naïve status | X | | | | | | | | | | | | |
| CDC classification | X | X | | | | | | | | | | | See Section 8.2 for more information |
| HIV-associated conditions | X | X | X | X | X | X | X | X | X | X | X | | See Section 8.2 for more information |
| Plasma for HIV-1 genotype/phenotype ⁴ | | X | X | X | | X | | X | X | X | X | | See Section 8.8 for more information |
| HIV-1 RNA | X | X | X | X | | X | | X | X | X | X | X | See Section 8.2 for more information |
| Physical examination including height and weight ⁵ | X | X | | | | | | X | | | | X | See Section 8.3.1 for more information |
| Vital signs | X | X | X | X | | X | | X | X | X | X | X | See Section 8.3.2 for more information |
| C-SSRS Administration | X | | | | | | | X | | | | X | See Section 8.3.6 for more information |
| ECG: single reading | X | | | | | | | | | | | | See Section 8.3.3 for more information |

CONFIDENTIAL

212580

Protocol Amendment 1 Final

| Procedure ¹ | Screening ² (7-14 days before Day 1) | Study Intervention Period Days 1-7 | | | | | | Post-Study Intervention Follow-up Days 8-21 | | | Follow-up/ED ¹⁵ | Notes ED = early discontinuation/withdrawal | |
|---|--|------------------------------------|----------------|---|-----------------------|---|-----------------------|---|----------------|-----------------------|----------------------------|--|---|
| | | Day 1 | Day 2 | Days 3 and 4 1 clinic visit and 1 virtual ³ | | Days 5 and 6 1 clinic visit and 1 virtual ³ | | Day 7 | Day 8 | Day 14 (+/- 1 day) | Day 21 (+/- 1 day) | | |
| | | Clinic visit 1 | Clinic visit 2 | Clinic visit 3 | Virtual ¹⁴ | Clinic visit 4 | Virtual ¹⁴ | Clinic visit 5 | Clinic visit 6 | Clinic visit 7 | Clinic visit 8 | Clinic visit 9 | |
| ECG: single reading pre-dose ¹³ | | | X | X | | X | | X | X | | | X | See Section 8.3.3 for more information |
| ECG: triplicate reading pre-dose | | X | | | | | | | | | | | See Section 8.3.3 for more information |
| ECG: single reading post-dose at 5, 7, 8 and 9 h | | X | | | | | | X ⁶ | | | | | See Section 8.3.3 for more information |
| Confirmation of PONCBP (female participants) | X | | | | | | | | | | | | See Section 10.4.1.1 for more information |

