5. Complete Physical Exam performed at Screening and Clinic Visit 9. At all other clinic visits perform a Brief Physical Exam including, at a minimum, assessments of the Skin, Heart, Lungs, and Abdomen (liver and spleen). Any abnormalities to be recorded as AEs. Height measured at Screening only, weight measured at all indicated visits.
6. ECG reading at 5, 7, 8 and 9 h post-dose on Day 7 applies to Part 1A and optional QD cohorts in Part 2 only.
7. Clinical chemistry includes a lipid panel (total cholesterol, HDL, LDL and triglycerides). Blood collection for Clinical Chemistry should be collected after a minimum of an 8 hour fast on Days 1, 8 and 25 for fasting lipid assessment.
8. Plasma samples for storage will be collected at each visit starting at Day 1, including unscheduled visits. These samples will be used when needed, such as when samples are lost or where quantity is insufficient for testing. In the event samples are not used by study completion, they will be utilized for additional research on antiretroviral resistance and/or HIV-1 disease biology/host immune response (excluding any human genetic testing).
9. Log in to RAMOS NG at Screening to complete registration for participant ID assignment. Register any screen fails in RAMOS NG. Log in to RAMOS NG on Day 1 (Visit 1) and for Part 1A and optional QD cohorts in Part 2 on Day 2 (Visit 2) to dispense blinded study treatment. Subsequently log-in to RAMOS NG for study treatment supply as needed. If a participant is discontinued from the study early, log in to RAMOS NG to record the discontinuation.

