5.2. Exclusion criteria

Participants are excluded from the study if any of the following criteria apply:

Medical Conditions

1. Any evidence of an active Centers for Disease Control and Prevention (CDC) Stage 3 disease [[CDC](#), 2014], except cutaneous Kaposi's sarcoma not requiring systemic therapy during the study;
2. Ongoing malignancy other than cutaneous Kaposi's sarcoma, basal cell carcinoma, or resected, non-invasive cutaneous squamous cell carcinoma, or cervical, anal or penile intraepithelial neoplasia; or other localized malignancies require agreement between the investigator and the study medical monitor for inclusion of the participant prior to randomization. Treatment with radiation therapy or cytotoxic chemotherapeutic agents within 30 days of study drug administration or anticipated need for such treatment within the study;
3. Any history of significant underlying psychiatric disorder, in the opinion of the Investigator or Medical Monitor, including but not limited to schizophrenia, bipolar disorder with or without psychotic symptoms, other psychotic disorders, or schizotypal (personality) disorder; or a clinical assessment of suicidality based on the responses on the C-SSRS. Participants' history of suicidal behaviour and/or suicidal ideation should be considered when evaluating for suicide risk;
4. Any history of major depressive disorder with or without suicidal features, or anxiety disorders, that required medical intervention (pharmacologic or not) such as hospitalization or other inpatient treatment and/or chronic (>6 months) outpatient treatment;

Note: Participants with other conditions such as adjustment disorder or dysthymia that have required shorter term medical therapy (<6 months) without inpatient treatment and are currently well-controlled clinically or resolved may be considered for entry after discussion and agreement with the Medical Monitor.

5. Any pre-existing physical or other psychiatric condition (including alcohol or drug abuse) which, in the opinion of the Investigator or Medical Monitor (with or without psychiatric evaluation), may interfere with the participant's ability to comply with the dosing schedule and/or protocol evaluations or which may compromise the safety of the participant;
6. Current or chronic history of liver disease or known hepatic or biliary abnormalities (with the exception of Gilbert's syndrome or asymptomatic gallstones);

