8.4.1. Time period and frequency for collecting AE and SAE information

All SAEs will be collected from the signing of the ICF until the final follow-up visit at the time points specified in the SoA.

All AEs will be collected from the start of study intervention until the final follow-up visit at the timepoints specified in the SoA.

Medical occurrences that begin before the start of study intervention but after obtaining informed consent will be recorded as medical history/current medical conditions, not as AEs.

All SAEs will be recorded and reported to the sponsor or designee immediately and under no circumstance should this exceed 24 h, as indicated in Section 10.3. The investigator will submit any updated SAE data to the sponsor within 24 h of it being available.

A poststudy AE/SAE is defined as any event that occurs outside of the AE/SAE reporting period defined in Section 8.4.1.

Investigators are not obligated to actively seek information on AEs or SAEs after conclusion of the study participation. However, if the investigator learns of any SAE, including a death, after a participant has been discharged from the study, the investigator must record it in the medical records. If the investigator considers the event to be reasonably related to the study intervention or study participation, the investigator must promptly notify the sponsor.

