The disease/disorder being studied or expected progression, signs, or symptoms of the disease/disorder being studied, unless more severe than expected for the participant's condition.

Medical or surgical procedure (e.g., endoscopy, appendectomy): the condition that leads to the procedure is the AE.

Situations in which an untoward medical occurrence did not occur (social and/or convenience admission to a hospital, admission for routine examination.).

Anticipated day-to-day fluctuations of pre-existing disease(s) or condition(s) present or detected at the start of the study that do not worsen. Pre-existing diseases will be recorded in the medical history section of the eCRF.

Hospitalization for elective treatment of a pre-existing condition (known or diagnosed before signing the informed consent) that did not worsen from baseline.

DRE typically associated with the disease under study. These events will be recorded in the participant's eCRF and will be monitored by the SRT on a routine basis.

However, if 1 or both of the following conditions apply, then the event should be reported promptly to GSK as an SAE (see Section [8.4.8](#)):

The event is, in the investigator's opinion, of greater intensity, frequency, or duration than expected for the individual participant, or

The investigator considers that there is a reasonable possibility that the event was related to the administration of the study intervention

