### **6.3. Appendix 2 Data Derivations Rule**

#### **6.3.1. Study Period**

Assessments and events will be classified according to the time of occurrence relative to the study intervention period.

**Pre-Treatment** is defined as time prior to the first dose of study intervention.

**On-Treatment Period Days 1-8** is defined as time from first study intervention dose (typically Day 1) to start of cART treatment (typically Day 8).

- If time of assessment or time of study intervention is not collected, Day 1 assessments other than AEs are considered to have occurred prior to study intervention dose and therefore considered on Pre-Intervention period, whereas AEs with Day 1 onset are considered to have occurred after study intervention dose and therefore considered on Monotherapy period.

**Post-Treatment Period Days 8- 25** is defined as time from first dose of cART treatment until study completion or withdrawal

- If time of assessment or time of cART initiation is not collected, Day 8 assessments other than AEs are considered to have occurred prior to cART initiation and therefore considered on on-treatment period, whereas AEs with Day 8 onset are considered to have occurred after cART initiation and therefore considered on Follow-Up period.

For concomitant medications, study periods will be defined as follows:

	Pre-Treatment	Monotherapy	Follow-Up	Pre-Treatment	cART	Follow-Up
(a)	x—x			Y	N	N
(b)	x	—x		Y 	Y 	N
(c)	x	—	—x	Y 	Y 	Y 
(d)		x—x		N	Y 	N
(e)		x—	—x	N	Y	Y
(f)			x—x	N	N	Y
(g)	?—x			Y	N	N
(h)	?	—x		Y*	Y	N
(i)	?	—	—x	Y*	Y*	Y*
(j)	x	—	?	Y	Y**	Y**
(k)		x—	?	N	Y	Y**
(l)			x—?	N	N	Y
(m)	?	—	?	Y***	Y***	Y***
(n)	x	x		Y	Y	N
(o)	?	x		Y	Y	N
(p)		x—x		N	Y	N
(q)	x	—	x	N	Y 	Y
(r)		x	—?	N	N	Y**
(s)		x	—x	N	N	Y
(t)	x	x		N	Y	Y

x = start/stop date of medication

? = missing start/stop date of medication

\* If a medication is stopped during the Monotherapy period or during the Follow-Up period and no start date is recorded it will be assumed that the medication was ongoing from the Pre-Intervention period

\*\* If a medication is started Pre-Intervention or on Monotherapy and no stop date is recorded then usage will be assumed to be ongoing for the remainder of the study

\*\*\* If a medication has no start or stop date it will be assumed that the medication was ongoing from the Pre-Intervention period to the Follow-Up period

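### Schedule of Activities footnote 5 has sites record every physical-examination abnormality as an AE, which contradicts the protocol's own AE rules and can put non-qualifying findings into the AE tables

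*Protocol*

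**What the plan says.** The row "Physical examination including height and weight" in the Schedule of Activities (protocol Section 1.3, Table 1) is marked at Screening, Day 1, Day 7 and Day 25 and carries footnote 5. The footnote begins "Complete Physical Exam performed at Screening and Clinic Visit 9", asks for a brief examination (skin, heart, lungs, abdomen) at other visits, and then instructs: "Any abnormalities to be recorded as AEs".

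Other parts of the plan set different rules for the same findings:

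- Protocol Section 8.4.1: "All AEs will be collected from the start of study intervention until the final follow-up visit at the timepoints specified in the SoA". Occurrences between consent and first dose "will be recorded as medical history/current medical conditions, not as AEs". SAP 6.1.5 repeats this.
- Protocol Section 8.1.2 places signs and conditions that precede the first dose under medical history.
- Protocol Section 10.3.1 makes an abnormal safety assessment an AE if the investigator judges it clinically significant. Among events that are not AEs it lists "Anticipated day-to-day fluctuations of pre-existing disease(s) or condition(s) present or detected at the start of the study that do not worsen".

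On counting, SAP 4.3.1.2 tabulates AEs for the treatment period and repeats selected displays for Follow-Up and for both periods together. It also provides a listing of all AEs.

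**The concern.** Footnote 5 is attached to the examination itself, so it is what site staff are likely to read when they do the exam. Taken literally, it turns any abnormality at any of the four marked visits into an AE, including two visits that fall before or on the day of first dose. A site cannot obey both the footnote and Section 8.4.1 for a pre-dose finding, or both the footnote and Section 10.3.1 for a trivial one.

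At stake is whether the AE tables measure one thing. If some sites follow the footnote and others follow Appendix 3, AE incidence partly reflects site practice. In cohorts this small, one misrecorded participant visibly moves a percentage, and AE incidence and severity through Day 25 is a stated (exploratory) endpoint.

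**Working it through.** The plan gives no figure to reproduce here. The check sets the rules side by side, then follows a recorded finding through the SAP.

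**1. Is there a contradiction?**

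| Finding | Footnote 5 | Other rule |
|---|---|---|
| Present at Screening | AE | Medical history (8.1.2, 8.4.1, SAP 6.1.5) |
| Present before first dose on Day 1 | AE | Medical history (same sections) |
| Stable pre-existing condition seen at Day 7 or 25 | AE | Not an AE (10.3.1) |
| New at Day 7 or 25, not clinically significant | AE | Not an AE (10.3.1) |
| New or worsened, clinically significant | AE | AE |

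Physical examination is one of the safety assessments in Section 8.3, so the significance test of 10.3.1 applies to it. The footnote and the other rules agree only in the last row.

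**2. Which records reach the AE tables?**

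- *Screening finding with a full pre-dose onset date.* SAP 6.3.1 classes it as Pre-Treatment, and SAP 4.3.1.2 describes no Pre-Treatment AE table. It reaches only the listing.
- *Day 7 or Day 25 finding.* Both exams follow first dose. A new but insignificant finding is counted directly. An unchanged one is counted if its onset is entered as the exam date; the footnote does not say how to date it.
- *Day 1 finding.* When the time of assessment or of study intervention is not collected, SAP 6.3.1 says "AEs with Day 1 onset are considered to have occurred after study intervention dose and therefore considered on Monotherapy period". Under the same rule, other untimed Day 1 assessments are treated as pre-dose. An untimed Day 1 exam can therefore be classed as pre-dose while the AE drawn from it is classed as on treatment.
- *Incomplete start date.* SAP 6.3.5 sets an AE start date with no day, in the month of first dose, to the first-dose date. It does the same for a date with no day or month in the year of first dose. The exception is a full stop date before dosing. An ongoing finding has no stop date, so a long-standing finding with a vague onset in that month or year becomes a Day 1 AE.

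**3. Size per participant.** Inputs are the cohort sizes in SAP 1.2: 6 per active cohort; placebo 1 (Part 1A) + 1 (Part 1B) + 1 (Part 2) = 3.

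- Active cohort: 1/6 = 16.7 percentage points.
- Placebo pooled over both parts: 1/3 = 33.3 percentage points.

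These apply to a participant whose only AE is spurious. The tables count participants, so overall incidence does not change if that participant has another AE in the period.

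**The case against.** The strongest reply is that footnote 5 is shorthand, that Section 8.4.1 and Appendix 3 are the governing AE rules, and that the SAP largely contains the damage. Much of this stands.

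- A reader might infer that all pre-existing findings enter the AE counts. The documents do not support that: a fully dated Screening finding stays out of the tables.
- A reader might infer that every Day 1 finding is counted as on treatment. The default applies only when a time is missing, and protocol Section 6.5 has in-clinic dose times recorded. The visible text also does not say the Day 1 exam is pre-dose; footnote 1's pre-dose order omits it. If the exam follows dosing, 10.3.1 makes a newly detected condition a valid AE even if it was present earlier.
- Cutaneous Kaposi's sarcoma looks like a natural example, because exclusion criterion 1 bars active CDC Stage 3 disease "except cutaneous Kaposi's sarcoma not requiring systemic therapy during the study". But Section 8.4.7 sends listed HIV conditions to the HIV-associated conditions page, with stated exceptions, and 10.3.1 places them outside the AE definition.
- One could assume a prevalence of exam abnormalities and compute the chance that a cohort carries a spurious AE. That would be a ceiling: it supposes that every site follows the footnote and every such finding is dated on treatment. Entrants must also be overtly healthy apart from HIV.
- The exposed endpoint is exploratory, and the study tests no hypothesis.

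These points limit the size. They do not reconcile the footnote with the sections it contradicts, and they leave the Day 7 and Day 25 exams, the untimed Day 1 onset and the imputed start date open. I found no requirement in the documents that AE onset time be collected.

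**Conclusion.** The contradiction is real and stands in current protocol text. Footnote 5 conflicts with protocol Sections 8.1.2, 8.4.1 and 10.3.1 and with SAP 6.1.5, on both timing and clinical significance.

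The consequence is conditional. It needs sites to follow the footnote, and then one of three routes: a Day 7 or Day 25 finding that fails the 10.3.1 test, a Day 1 onset with a missing time, or an incomplete start date moved to first dose. The effect falls on the overall AE and severity tables and the exploratory AE endpoint through Day 25. The secondary endpoint (SAEs, deaths and AEs leading to discontinuation through Day 8) is little affected, since a stable or trivial finding is unlikely to be serious or to stop treatment.

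Each participant whose only AE is spurious shifts the overall percentage by the amounts worked out above. How many there would be cannot be derived from the documents. The placebo figure assumes that the three placebo participants are pooled.

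**What to change.** Replace the last instruction in footnote 5 with a two-part rule. Abnormalities present at Screening or before first dose are recorded as medical history (Sections 8.1.2, 8.4.1) or, where applicable, on the HIV-associated conditions page (Section 8.4.7). After first dose, abnormalities that meet Section 10.3.1 are recorded as AEs.

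In SAP 6.3.1 and 6.3.5, add that an AE is not defaulted to on treatment when its finding is documented in medical history or at an assessment known to be pre-dose.

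Before database lock, check AEs dated on or before Day 1 against medical history. The SAP's interim-analysis footnote shows that Part 1 data already exist, and a change to the protocol footnote cannot alter those records.

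The cost is one sentence in an amendment or site memo, one SAP clause, and a manual reconciliation over a planned 20 + 7 = 27 participants. No new assessment is needed, but the SAP exception does need each affected AE to be traceable to a medical-history entry or to an exam of known timing.

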| Hepatitis B and C serology | X | | | | | | | | | | | | If test result available from within 3 months before first dose of study intervention, testing at screening is not required. See Section 8.3.4 for more information |
| Hematology/Chemistry/Urine | X | X | | X | | X | | X | X | X | X | X | See Section 8.3.4 for more information |
| Fasting lipids and glucose (minimum 8 h) ⁷ | | X | | | | | | X | | | | X | See Section 8.3.4 for more information |
| Lymphocyte T-cell subsets (CD4/CD8) | X | | | | | | | | X | | | | See Section 8.3.4 for more information |

CONFIDENTIAL

212580

Protocol Amendment 1 Final

| Procedure ¹ | Screening ² (7-14 days before Day 1) | Study Intervention Period Days 1-7 | | | | | | Post-Study Intervention Follow-up Days 8-21 | | | Follow-up/ED ¹⁵ | Notes ED = early discontinuation/withdrawal | |
|--|--|------------------------------------|-----------------|---|-----------------------|---|-----------------------|---|----------------|-----------------------|----------------------------|--|---|
| | | Day 1 | Day 2 | Days 3 and 4 1 clinic visit and 1 virtual ³ | | Days 5 and 6 1 clinic visit and 1 virtual ³ | | Day 7 | Day 8 | Day 14 (+/- 1 day) | Day 21 (+/- 1 day) | | |
| | | Clinic visit 1 | Clinic visit 2 | Clinic visit 3 | Virtual ¹⁴ | Clinic visit 4 | Virtual ¹⁴ | Clinic visit 5 | Clinic visit 6 | Clinic visit 7 | Clinic visit 8 | | |
| Syphilis RPR | X | | | | | | | | | | | | See Section 8.3.4 for more information |
| Plasma for storage ⁸ | | X | X | X | | X | | X | X | X | X | X | See Section 8.3.4 for more information |
| IWRS (RAMOS NG) activity ⁹ | X | X | X | | | | | | | | | | See Section 6.3 for more information |
| Optional genetic sample | | X | | | | | | | | | | | A separate genetics ICF is required |
| Observed administration of study intervention | | X | X ¹⁰ | X ¹⁰ | X ¹⁰ | X ¹⁰ | X ¹⁰ | X ¹⁰ | | | | | See Section 6.1 for more information |
| Observed dosing with cART, and eCRF completion ¹¹ | | | | | | | | | X | X | X | X | See Section 6.1 for more information |
| AE review | | ←————→ | | | | | | | | | | | See Section 10.3.7 for more information |
| SAE review | | ←————→ | | | | | | | | | | | See Section 10.3.7 for more information |
| Concomitant medication review | | ←————→ | | | | | | | | | | | See Section 6.9 for more information |
| Serial PK sampling ¹² | | X | | | | | | X | | | | | See Section 8.5 for more information |

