5.3. Lifestyle considerations

5.3.1. Meals and dietary restrictions

Participants will be required to fast for at least 8 h [overnight] prior to the morning check-in at clinic visits on Days 1-8 and Day 25 in Part 1A (and optional Part 2A) and Days 1, 8 and 25 in Part 1B (and optional Part 2B). Procedures will be performed in the following order: C-SSRS, ECG, Vital Signs and Blood Draws in a fasted state. On days when participants take the study intervention, each dose will be taken with approximately 240 mL (8 ounce) water following ingestion of a moderate calorie and fat meal, to be completed within approximately 25 minutes just prior to dosing, with dose administration to occur within 5 minutes of completion of meal consumption. This includes the virtual visits where participants must have completed their meal within approximately 25 minutes of their scheduled call with site staff, with dose administration to occur within 5 minutes of completion of meal consumption.

Refrain from consumption of red wine, Seville oranges, grapefruit, or grapefruit juice, pomelos, exotic citrus fruits, grapefruit hybrids, or fruit juices from 3 days before the start of study intervention until Day 8.

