| Follicle stimulating hormone (FSH) and estradiol (only for instances when postmenopausal status is questionable) | | | |
| 
a) Glucose and lipid profile can be non-fasting except on Days 1, 8 and 25, as indicated in Section 1.3.
 
b) Glomerular filtration rate (eGFR) will be estimated by the central laboratory using the refitted, race-neutral Chronic Kidney Disease Epidemiology Collaboration (CKD-EPIcr_R) method [Delgado, 2022]. In addition, GFR will be estimated by the central laboratory using the refitted, race-neutral CKD-EPI-cystatin C [Delgado, 2022] at Day 1 and when indicated by renal toxicity criteria.
 
c) For fasting lipids assessments, an overnight fast is preferred; however, a minimum of a 6-hour fast is acceptable for participants with afternoon appointments.
 
d) HBV DNA will only be performed for participants with a positive anti-HBc and negative HbsAg and negative anti-HBs (past and/or current evidence).
 
e) Details of liver chemistry stopping criteria and required actions and follow-up assessments after liver stopping or monitoring event are given in Section 7.1.1 and Section 10.6. In addition, the laboratory may perform Hepatitis E IgM and Cytomegalovirus IGM if required in the event of a liver event. All events of ALT $\geq 3 \times$ upper limit of normal (ULN) and total bilirubin $\geq 2 \times$ ULN ($>35\%$ direct bilirubin) or ALT $\geq 3 \times$ ULN and INR > 1.5, if INR measured, which may indicate severe liver injury (possible Hy's law), must be reported to GSK/ViiV Healthcare in an expedited manner (excluding studies of hepatic impairment or cirrhosis).
 
f) Laboratory tests for eligibility may be performed by local laboratory in exceptional circumstances, however, central laboratory samples must also be collected at the screening visit. The results of each test used for eligibility must be entered in the eCRF.
 | | | |
| The addresses of the clinical laboratories in charge of human biological sample testing are provided in a separate document ('List of clinical laboratories used for human biological sample analysis') and stored in TMF at the time of the protocol finalization. | | | |

10.3. Appendix 3: AEs and SAEs: Definitions and procedures for recording, evaluating, follow-up, and reporting**10.3.1. Definition of AE**

| AE definition |
|---|

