A summary, i.e. number of participants and percentages for each of the following bile acid categories “≤1 xULN”, “>1x to ≤1 xULN”, “>3x to ≤5 xULN”, “>5x to ≤10 xULN”, “>10x ULN”, will be provided at worst case post-baseline record.

A summary of participants with shifts in laboratory grade from Baseline to worst case post-baseline will also be created for selected gradable lab parameters (e.g. lipids etc.). For selected non-gradable lab parameters (e.g. bile acid), shifts from baseline to worst-case post-baseline relative to categories defined based on xULN (see paragraph above) will be created.

A summary of hepatobiliary laboratory abnormalities will also be provided to identify participants, in particular possible Hy’s Law participants, for further clinical review.

All the summaries above will be produced while participants are under the monotherapy period, as well as overall (i.e. monotherapy and Follow-Up periods).

A listing of all laboratory data and a listing of all urinalysis data will be created.

All displays on hematology, coagulation, urinalysis and chemistry laboratory parameters are included in the OPS.

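### The Schedule of Activities marks a fasting sample on Day 7 against Day 8 elsewhere; separately, required fasting at chemistry draws differs by dosing schedule and the SAP's worst-case lipid and glucose displays ignore it

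*Protocol*

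**What the plan says.** **Fasting days in the Protocol**

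- Section 1.3, Table 1: the row "Fasting lipids and glucose (minimum 8 h" is marked on Day 1, Day 7 and Day 25. Day 8 is blank.
- Section 1.3, footnote 7 to that row: "Blood collection for Clinical Chemistry should be collected after a minimum of an 8 hour fast on Days 1, 8 and 25". The same footnote makes the lipid panel part of clinical chemistry.
- Section 10.2, Table 10 note a: "Glucose and lipid profile can be non-fasting except on Days 1, 8 and 25, as indicated in Section 1.3".
- Section 5.3.1: the overnight fast applies on "Days 1-8 and Day 25 in Part 1A (and optional Part 2A) and Days 1, 8 and 25 in Part 1B", with optional Part 2B treated like Part 1B.
- Section 10.7: lipid samples must be fasted, with the days left to the Schedule of Activities.

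**Use of the results in the SAP**

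- Section 4.1.2: baseline is the last non-missing pre-dose value, normally Day 1.
- Section 4.5.2: non-liver chemistry is summarised as change from baseline at each visit and as maximum grade increase, using the method of Section 4.4.2, which counts planned and unscheduled assessments alike.
- Section 4.5.2 also plans that "shifts in laboratory grade from Baseline to worst case post-baseline will also be created for selected gradable lab parameters (e.g. lipids etc".
- These displays are made for the monotherapy period and for monotherapy plus follow-up. The SAP text has no rule on fasting status.

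**The concern.** A site reading the Schedule row would plan a fasted sample on Day 7. A single-dose participant who follows Section 5.3.1 has no instruction to fast that day. Section 10.7 sends the reader back to the row that disagrees with its own footnote, so it does not settle the matter.

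The analysis raises a different question. A worst-case rule picks the most extreme value from all draws. If one dosing schedule contributes only draws with a required fast and the other contributes several without one, the grade-shift table compares groups under different dietary conditions, both against a fasted baseline. An apparent metabolic signal, or an apparent difference between dosing schedules, could then be partly diet. Placebo does not resolve this: Part 1 has one placebo participant in 1A and one in 1B, and the SAP summarises placebo as one group.

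**Working it through.** The plan gives no figure to reproduce. The check is a count of Schedule columns crossed with the fasting days in Section 5.3.1.

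**Step 1. Is the mark really under Day 7?** The columns run: Screening, Day 1, Day 2, Clinic Visit 3 (Day 3 or 4), virtual, Clinic Visit 4 (Day 5 or 6), virtual, Day 7, Day 8, Day 14, Day 21, Day 25.

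- Fasting row: Screening blank, Day 1 marked, five blanks, a mark in column 8, three blanks, a mark in column 12.
- Post-dose ECG row: its second mark is also in column 8 and carries footnote 6, which says "ECG reading at 5, 7, 8 and 9 h post-dose on Day 7 applies to Part 1A". Column 8 is therefore Day 7.
- Serial PK row: marks in the same two columns as the ECG row. Footnote 12 names Days 1 and 7.
- CD4 row: Screening marked, seven blanks, then a mark in column 9, which is Day 8.

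The Day 7 position is therefore not a column shift from reading the PDF.

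**Step 2. Designated fasting visits against the diet section**

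| Fasting visits taken from | Once-daily: fast required | Single-dose: fast required |
|---|---|---|
| Schedule row (Days 1, 7, 25) | 3 of 3 | 2 of 3 (not Day 7) |
| Footnote 7 and Table 10 (Days 1, 8, 25) | 3 of 3 | 3 of 3 |

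The once-daily fasting range covers both Day 7 and Day 8, so the conflict with Section 5.3.1 is confined to the single-dose cohorts.

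**Step 3. Chemistry draws, each including lipids and glucose.** The chemistry row has seven post-baseline visits. SAP 6.3.1 ends the on-treatment period at the start of cART, so the pre-cART Day 8 sample counts as on-treatment.

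| Draw | Once-daily | Single-dose |
|---|---|---|
| Clinic Visit 3 | required | not required |
| Clinic Visit 4 | required | not required |
| Day 7 | required | not required |
| Day 8 | required | required |
| Day 14 | not required | not required |
| Day 21 | not required | not required |
| Day 25 | required | required |

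- On-treatment: once-daily 4/4 = 100%; single-dose 1/4 = 25%.
- All post-baseline: once-daily 5/7 = 71%; single-dose 2/7 = 29%.
- Draws without a required fast that can supply the worst value: monotherapy period, 4 − 4 = 0 against 4 − 1 = 3; overall, 7 − 5 = 2 against 7 − 2 = 5.

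**Step 4. Does correcting the Schedule row remove the imbalance?** No. Moving the mark to Day 8 leaves Step 3 unchanged, because those counts come from the chemistry row, Section 5.3.1 and the permission in Table 10 note a.

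**Step 5. Who is affected?** Part 1B has 6 + 1 = 7 of the 20 Part 1 participants, plus any Part 2B cohort. The visible SAP text does not show whether its single Part 2 cohort is once-daily or single-dose.

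**The case against.** The strongest reply is that little is lost. Chemistry is drawn on Day 8 in every cohort, a fast is required that day in every cohort, and the SAP summarises change from baseline by visit with Day 8 as its own window. A like-for-like fasted comparison on Days 8 and 25 is therefore already planned. Lipids and glucose are not listed among the primary, secondary or exploratory endpoints, and safety analysis is descriptive. All of this stands and limits the weight of the point.

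Several stronger readings are tempting, and the documents do not support them:

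- *The Day 7/Day 8 mismatch causes the imbalance between schedules.* It does not (Step 4).
- *A site following the Schedule row would take an unfasted sample.* The row itself asks for an 8-hour fast. The fault is that Section 5.3.1 gives single-dose participants no matching instruction.
- *Single-dose samples were mostly unfasted.* The documents show only that fasting was not required. Actual status at these visits is unknown.
- *The overall display sets fed values in one schedule against fasted values in the other.* Once-daily cohorts also have Days 14 and 21 without a required fast. The clean contrast holds only for the monotherapy period.

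It is also fair to say that the size of any effect on grades cannot be computed. The Protocol's grading appendix reproduces clinical parameters only, so lipid and glucose thresholds are not visible. The SAP leaves display details to a separate document, so the absence of a fasting rule can be stated only for the SAP text.

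The reply does not remove the inconsistency in current text, or the fact that the worst-case displays, unlike the by-visit summary, mix draws with and without a required fast.

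**Conclusion.** Both points hold, and they are independent.

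1. The Schedule row contradicts its own footnote and Table 10 note a. It also places a fasting sample on a day when Section 5.3.1 does not tell single-dose participants to fast, and Section 10.7 relies on the Schedule.
2. The monotherapy-period worst-case display for lipids and glucose draws on samples with a required fast at 4 of 4 visits in once-daily cohorts and 1 of 4 in single-dose cohorts, so a difference between schedules in that table can reflect diet. The overall display has the same problem in weaker form, 5 of 7 against 2 of 7.

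This rests on three assumptions: the Day 1 baseline is fasted as required, the Day 8 sample precedes cART, and glucose is among the DAIDS-graded parameters in Section 4.5.2 (the SAP names lipids explicitly but not glucose). The counts describe what is required, not what happened, and no change in any grade is estimated. The matter deserves correction because it is cheap and the SAP rule also covers Part 1 data already collected. It does not bear on the primary or secondary endpoints.

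**What to change.** **Protocol.** Reconcile the Schedule row, footnote 7, Table 10 note a, Section 5.3.1 and Section 10.7 so that the designated fasting visits and the fasting instructions agree for every cohort. The same edit should settle the minimum fast: Table 10 note c accepts 6 hours for afternoon appointments, while the Schedule and Section 5.3.1 ask for at least 8.

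**SAP 4.5.2.** Add change-from-baseline and grade-shift displays for lipids and glucose, limited to samples on the days when the Protocol requires fasting in all cohorts (Days 1, 8 and 25 as Section 5.3.1 now stands). Keep the planned all-draw worst-case tables and the listings, and flag values from days without a required fast. The worst-case tables should not themselves be restricted to the fasting days, because that would drop abnormalities seen at other or unscheduled draws from the safety tables.

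**Cost.** A few extra displays, one flag derived from study day and cohort, and a text correction. No additional sample is needed.
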